### **Outcome Data Collection**

*Primary outcomes (hospitalizations and arrests).* Hospitalization data will be collected from three sources: the Georgia Department of Behavioral Health and Developmental Disabilities (DBHDD, the State's mental health agency), the CSU in Savannah, and the CSU in Brunswick. Because DBHDD operates all state psychiatric hospitals, they have complete admission and discharge data for the study timeframe. However, DBHDD only collected CSU data beginning in January 2017; as such, the two CSUs serving as referral sites will also provide admission and discharge data for the full study period.

Arrest data will be provided by the Georgia Crime Information Center (GCIC), within the Georgia Bureau of Investigation (the lead state law enforcement agency), in the form of the participants' record of arrests and prosecutions (RAP sheets). GCIC receives monthly arrest reports from >600 state and local law enforcement agencies; this information is stored in GCIC's crime database and is summarized in the RAP sheet. To test our arrest-related hypotheses, we will extract all arrests for the 12 months after enrollment. Arrest data will be available for all participants.

*Secondary outcomes (housing and recovery).* Data collection for the two secondary outcomes will be collected in-person, though retention is expected to be difficult based on the serious psychosocial impairment of the study sample and experience in the initial study. Two housing-related measures will be used. The *Housing Satisfaction Scale* (HSS) has 19 items covering choice, safety, privacy, and proximity. The *Housing Instability Index* (HII) is a sum of 10 items that ask participants about their housing situations over the past six months; the time frame was adapted to four months for this study to match the follow-up timepoints.

To thoroughly assess recovery, we will examine five measures of constructs aligned with recent conceptualizations of recovery and the goals of ODR. First, the *Multnomah Community Ability Scale* (MCAS) is a 17-item instrument that measures social and community functioning, with documented good inter-rater and test-retest reliability, and validity. We added five items covering several areas deemed important for the study's purposes. Second, the *Maryland Assessment of Recovery in People with Serious Mental Illness* (MARS) is a 25-item instrument addressing recovery experiences, with documented excellent internal consistency and test-retest reliability, as well as construct validity and divergent validity. Third, the *Herth Hope Scale* (HHS) is a 30-item measure widely used to assess hope, and with well-documented psychometric properties. Fourth, the *Empowerment Scale* (ES) is a 28-item measure assessing self-esteem, perceived power, optimism/control over the future, and related constructs, with documented reliability and validity. Finally, the 21-item Community Navigation Scale was developed for the initial and current study—preliminary psychometric research suggests good internal consistency reliability and construct validity.

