**A Trial of “Opening Doors to Recovery” for Persons with Serious Mental Illnesses**

**ClinicalTrials.gov: Identifier NCT04612777**

**09/13/2022**

**Revised 07/24/2024**

## Methods

### Participants

Enrollment will begin in December 2014 and continue until the target sample size is achieved, which is expected to take approximately three years. Adults with serious mental illnesses (SMI) will be recruited from three inpatient facilities: a state psychiatric hospital in Savannah, Georgia; a crisis stabilization unit (CSU) in Savannah; and a CSU in Brunswick, Georgia.

Eligibility criteria will include: (1) 18–65 years of age; (2) English speaking; (3) diagnosis of a psychotic or mood disorder (confirmed with the *Structured Clinical Interview for DSM-5 Disorders* (SCID-5); (4) two separate inpatient admissions, each for  $\geq 2$  days, in the past 12 months; (5) absence of intellectual disability or dementia; (6) capacity to provide informed consent; (7) being discharged to reside within one of seven counties with case management (CM) services provided by the public mental health agency hosting the research; (8) not currently receiving assertive community treatment (ACT) or CM; and (9) eligible to receive CM; i.e., unable to complete daily living activities in at least two areas, despite caregiver or behavioral health staff support, and requires assistance in one or more areas of managing their illness.

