### **Data Analyses**

Between-group comparisons will rely on intention-to-treat analyses. Analyses involving hospitalizations and arrests will be performed using both binomial and Poisson generalized linear models for binary outcomes and counts, respectively. Analyses of change in housing and recovery measures will be performed using linear mixed models on all available data at each timepoint. Time in months will be used as a continuous predictor (growth curves) with measures at baseline, 4-, 8-, and 12-months. For the primary outcome analysis (12-month endpoint) the model structure will include group (ODR vs. CM), time, and group-by-time interactions, with a random intercept for subject. For those measures that indicate significant 2-group differences, we will compare ODR against ICM specifically, to further define effects (post-hoc analyses). For count/duration of hospitalizations and number of arrests, we will do conditional tests (comparing only those with non-zero values) to reduce the effects of zero inflation and get meaningful effect sizes across groups.

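### The Poisson model for arrest counts needs standard errors that allow for overdispersion; a prior-arrest covariate is an optional gain in precision and its absence causes no bias

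*Combined protocol and SAP*

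**What the plan says.** Outcome Data Collection makes hospitalizations and arrests the primary outcomes. Arrest reports are held in the state agency's "crime database and is summarized in the RAP sheet", and the extraction is limited to follow-up: "To test our arrest-related hypotheses, we will extract all arrests for the 12 months after enrollment". The section expects complete arrest data. It does not say how far back the supplied record goes.

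Data Analyses states: "Analyses involving hospitalizations and arrests will be performed using both binomial and Poisson generalized linear models", for the yes/no outcome and the count respectively. It names no dispersion parameter, robust standard error, negative-binomial alternative or baseline covariate for these models.

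The only list of model terms is: "the model structure will include group (ODR vs. CM), time, and group-by-time interactions, with a random intercept for subject". It follows the text on the housing and recovery growth curves, which are fitted "with measures at baseline, 4-, 8-, and 12-months", yet it is introduced as the primary outcome analysis, so its scope is unclear.

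For event counts the section adds tests restricted to participants with at least one event, "to reduce the effects of zero inflation and get meaningful effect sizes across groups".

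Referral, Assessment, and Randomization describes 1:1 allocation in blocks of 2 or 4, with no stratification. No sample size, arrest rate, significance level, power or prior/follow-up correlation is given.

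**The concern.** Two separate things are at stake.

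- **Standard errors.** A Poisson model sets the variance equal to the mean. People differ in their risk of arrest, and the plan itself foresees too many zeros, so the variance is likely to exceed the mean. The model's own standard errors would then be too small, and the test on a primary outcome would reject too often when there is no effect.
- **Precision.** Prior arrests are the closest baseline measure of this outcome. The housing and recovery models use a pre-randomization value as their first timepoint; the arrest models do not. If prior arrests predict later ones, leaving them out makes the rate ratio noisier than it needs to be.

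**Working it through.** There is no stated figure to reproduce, so every rate, sample size and correlation below is an assumption.

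**1. Inputs.** From the plan: one complete 12-month count per person, 1:1 allocation, Poisson model. Assumed: two-sided 5% test; 120 per arm (60 and 200 as variants); rate ratio 0.7 where there is an effect; individual rates that follow a gamma distribution with shape k, with mean m0 arrests in the prior year and m in the control follow-up year.

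**2. False-positive rate of the plain Poisson test.** Var(Y) = m + m²/k = m·φ, with φ = 1 + m/k. With no effect the Poisson standard error is too small by a factor √φ, so the nominal 5% test rejects with probability 2[1 − Φ(1.96/√φ)].

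| Setting | m0 | m | k | φ | 1.96/√φ | False-positive rate |
|---|---|---|---|---|---|---|
| A | 1 | 0.6 | 0.5 | 2.20 | 1.321 | 18.6% |
| B | 1 | 0.6 | 1 | 1.60 | 1.550 | 12.1% |
| C | 0.6 | 0.4 | 0.5 | 1.80 | 1.461 | 14.4% |
| D | 1 | 1 | 1 | 2.00 | 1.386 | 16.6% |
| E | 2 | 1 | 2 | 1.50 | 1.600 | 11.0% |
| F | 0.5 | 0.3 | 1 | 1.30 | 1.719 | 8.6% |
| G | 0.5 | 0.5 | 2 | 1.25 | 1.753 | 8.0% |

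Simulated trials agree: about 7-19% with plain Poisson errors and 4-7% with robust errors. Adding prior arrests while keeping plain Poisson errors still gave about 6-18%.

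Log-normal differences between people (240 in total, 0.6 arrests per year, SD of log rate 0.7, 1.0 and 1.3) gave 10%, 16% and 29%. With no such differences the rate was 5.2%. Robust errors gave 4.8-6.3%.

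**3. Link to zero inflation.** If a share π of people can have no arrests and the rest are Poisson with mean λ, variance/mean = 1 + πλ, which exceeds 1. The gamma model gives the same picture: in setting A the expected share of zeros is 2.2^(−0.5) = 67%, against e^(−0.6) = 55% under Poisson.

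**4. Standard errors in setting A, 120 per arm, means 0.60 and 0.42.**

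- Poisson: √[1/(120×0.60) + 1/(120×0.42)] = 0.184 (simulated 0.186).
- Actual: √[(1/0.60 + 1/0.5 + 1/0.42 + 1/0.5)/120] = √(8.048/120) = 0.259 (simulated robust 0.258).
- With log(prior + 1) added: plain Poisson 0.188, robust 0.214.

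The covariate's gain is therefore invisible unless the standard errors are corrected as well.

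**5. Gain for counts from adjusting.** The linear approximation is a variance factor of 1 − r². Equivalent sample size is 1/(1 − fall).

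| r | Fall, 1 − r² rule | Fall, simulated | Equivalent extra participants | Power gain at 120 per arm |
|---|---|---|---|---|
| 0.4-0.6 | 16-36% | 12-32% | 1/0.88 to 1/0.68: 14-47% | 5-11 points |
| 0.2-0.3 | 4-9% | 1-10% | 1/0.99 to 1/0.90: 1-11% | about 1-2 points |
| 0.15 or less | about 2% or less | −0.4 to 1.9% | about 0-2% | −0.2 to +0.5 points |

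The reachable r depends on the arrest rates. If the individual rate is fully stable over time and there is no effect, r = √{[m0/(k+m0)]·[m/(k+m)]}. Setting A: √(0.667×0.545) = 0.60. Setting F: √(0.333×0.231) = 0.28. Setting G: √(0.2×0.2) = 0.20. In the settings tried, r of 0.4 or more arose only with 0.6-2 prior arrests per person per year.

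**6. Binary outcome.** The power gain is smaller, from about none (−1) to +4 points. With log-normal heterogeneity, power went from 55 to 57%, 45 to 47% and 33 to 36%. In setting A the log odds ratio was −0.301 unadjusted, −0.394 conditional on prior arrests and −0.300 after standardizing (SDs 0.281, 0.332 and 0.252). Standardizing keeps the unadjusted target.

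**7. Bias.** In the log-normal trials with a true log rate ratio of −0.511, the unadjusted estimate averaged −0.51 to −0.52.

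**The case against.** **The covariate is a matter of preference.** A randomized intention-to-treat comparison is not biased by leaving it out, and the documents give nothing to place the trial between no gain and a 32% fall in variance. This stands, so the covariate is optional. A reader might infer that the arrest comparison is biased or invalid without it; step 7 and the randomization argue against that.

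**The random intercept could absorb the overdispersion.** It could, if the arrest counts were fitted as a mixed model. But the plan calls the arrest models generalized linear models, and the listed terms need repeated times, while arrests are described as a single 12-month extraction. If the list is meant to cover arrests, the plan must say so.

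**The tests among those with events deal with the zeros.** They do not correct the standard error of the full-sample Poisson model. They also select on an outcome after randomization, so they are no longer a randomized comparison.

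**It may be too late.** "Enrollment will begin in December 2014"; about three years of enrollment plus 12 months of follow-up ends around the end of 2018, while the document is dated September 2022 and revised July 2024. Pre-specification therefore cannot be assumed. Equally, the documents do not say that outcomes had been seen by arm, so a reader should not infer that either.

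**The earlier data may not be in hand.** That the arrest record reaches back before enrollment is an inference from what such a record is. This stands as a condition on the optional part.

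**Conclusion.** The point holds in two parts of unequal weight.

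The main part is that the Poisson analysis of arrest counts has no safeguard against overdispersion, although the plan expects excess zeros. Under the gamma settings, at 0.3-1 arrests per year, the false-positive rate is about 7-19% instead of 5%; heavier-tailed heterogeneity could take it higher. This is conditional. The documents give no variance, so they do not support saying that the trial's arrest result is or will be a false positive. If the counts are close to Poisson, nothing is lost by the correction.

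The lesser part is that no prior-arrest covariate is named. The cost is possible precision only. It would be tempting to quote the largest power gain seen, about 15 points (200 per arm, counts, strong correlation), but that needs high arrest rates and a stable individual risk, neither of which the documents show. At a correlation of 0.15 or less the gain is about nil, and for the binary outcome it is at most about 4 points.

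Saying that the unadjusted comparison is valid is right only in the sense of no bias from the missing covariate. It does not extend to the plain Poisson standard errors or to the tests restricted to those with events.

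**What to change.** **Needed.** In Data Analyses, state that arrest counts will be analysed with robust (sandwich) standard errors or a negative-binomial model, and say whether the list of group, time and random-intercept terms applies to arrests. This is a wording change and needs no new data.

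**Optional.** First confirm that the supplied arrest records and the approvals cover the 12 months before enrollment, and whether outcomes have been seen by arm.

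- If they have not been seen: pre-specify log(prior arrests + 1) as a covariate in the arrest models, report a standardized (marginal) effect for the binary outcome, and keep the unadjusted results as supportive.
- If they have been seen: keep the unadjusted analysis as the planned one and label the adjusted analysis a sensitivity analysis.

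The optional part costs a longer extraction window, a check of record coverage and approvals, and a little more analysis. It should not be done without the standard-error change, because plain Poisson errors would hide the gain and still be too small.

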### **Recovery Summary Score (RSS)**

Because the recovery measures are likely to be highly correlated, we will derive a summary measure to conserve power, which we call the overall Recovery Summary Score (RSS), using principal component analysis (PCA) with possible rotation, and then calculating a patient-specific summary measure by standardizing each of the five measures and then averaging for each subject and timepoint.

### **Data Analyses**

Between-group comparisons will rely on intention-to-treat analyses. Analyses involving hospitalizations and arrests will be performed using both binomial and Poisson generalized linear models for binary outcomes and counts, respectively. Analyses of change in housing and recovery measures will be performed using linear mixed models on all available data at each timepoint. Time in months will be used as a continuous predictor (growth curves) with measures at baseline, 4-, 8-, and 12-months. For the primary outcome analysis (12-month endpoint) the model structure will include group (ODR vs. CM), time, and group-by-time interactions, with a random intercept for subject. For those measures that indicate significant 2-group differences, we will compare ODR against ICM specifically, to further define effects (post-hoc analyses). For count/duration of hospitalizations and number of arrests, we will do conditional tests (comparing only those with non-zero values) to reduce the effects of zero inflation and get meaningful effect sizes across groups.

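### The all-patient Poisson comparison of admission and arrest counts has no stated allowance for overdispersion, so its test is anti-conservative if the variance exceeds the mean and no random intercept applies

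*Combined protocol and SAP*

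**What the plan says.** Outcome Data Collection names hospitalizations and arrests as the primary outcomes. Data Analyses then says:

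- On the estimand: "Between-group comparisons will rely on intention-to-treat analyses".
- On the model: "Analyses involving hospitalizations and arrests will be performed using both binomial and Poisson generalized linear models for binary outcomes and counts, respectively". No dispersion parameter, robust variance or negative binomial alternative follows.
- On excess zeros: "For count/duration of hospitalizations and number of arrests, we will do conditional tests", restricted to participants with non-zero values, "to reduce the effects of zero inflation". No model is named for these tests.
- On a random effect, after the linear mixed model text for housing and recovery: "Time in months will be used as a continuous predictor (growth curves) with measures at baseline, 4-, 8-, and 12-months", and then "For the primary outcome analysis (12-month endpoint) the model structure will include group (ODR vs. CM), time, and group-by-time interactions, with a random intercept" for each subject.
- On what a significant result leads to: "For those measures that indicate significant 2-group differences, we will compare ODR against ICM specifically". The plan labels this step post hoc.

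The documents give no sample size, significance level, event rate or dispersion figure.

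**The concern.** A Poisson GLM sets the variance equal to the mean. Under the usual zero-inflated Poisson model, or when patients have different underlying rates, the variance is larger than the mean. The model-based standard error of the rate ratio is then too small, the confidence interval too narrow and the test too liberal. The plan itself expects excess zeros, but its only stated response is a comparison among participants with at least one event. That comparison leaves the all-patient standard error unchanged. It also selects on an outcome that arises after randomization, so it cannot stand in for the intention-to-treat comparison.

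At stake are the rate comparisons for two primary outcomes, and to a lesser degree the post hoc comparison with ICM that a significant result opens.

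**Working it through.** There is no figure in the plan to reproduce. Everything below rests on assumed count distributions, a two-sided 5% level, and 60 to 120 participants per arm with equal allocation (the 1:1 ratio is in Referral, Assessment, and Randomization).

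**Formula.** The Poisson model takes the variance of the log rate ratio as 1/(events in arm A) + 1/(events in arm B). If the variance-to-mean ratio is φ in both arms, the true variance is φ times that. The Wald statistic then has standard deviation √φ under the null, so

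- size ≈ 2 × (1 − Φ(1.96/√φ))
- interval width as a fraction of the correct width (log scale) = 1/√φ

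**Where φ comes from.**

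- Zero-inflated Poisson with mean m and share p of structural zeros: φ = 1 + p·m/(1 − p). With m = 0.5 and p = 0.4, φ = 1 + 0.2/0.6 = 1.33.
- Unequal rates: φ = 1 + Var(rate)/mean. Rates of 0.5 and 1.5 in equal halves give 1 + 0.25/1 = 1.25.

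**Size of the all-patient Poisson test.** Simulation used 20,000 null trials per setting.

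| Assumed counts | φ | Formula | Simulated |
|---|---|---|---|
| Zero-inflated, mean 0.3, 20% structural zeros | 1.075 | 5.9% | 5.3-5.9% |
| Rates 0.5 and 1.5, equal halves | 1.25 | 8.0% | 7.5-7.8% |
| Zero-inflated, mean 0.5, 40% | 1.33 | 9.0% | 8.4-8.9% |
| Negative binomial, mean 0.4 or 1 | 2 | 16.6% | 15.7-16.6% |
| Negative binomial, mean 1 | 3 | 25.8% | 25.2-25.6% |
| Zero-inflated, mean 1.5, 60% | 3.25 | 27.7% | 27.3-28.2% |

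At φ = 1.33, 2 and 3, nominal 95% intervals cover about 91%, 83% and 74%. Their widths are 0.87, 0.71 and 0.58 of the correct width.

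**Excess zeros alone.** Suppose 0, 1, 2 and 3 events occur in 40, 30, 20 and 10% of patients. The mean is 0.3 + 0.4 + 0.3 = 1.00, the mean square is 0.3 + 0.8 + 0.9 = 2.00, and the variance is 1.00. Zeros exceed the Poisson share (40% against 36.8%), but φ = 1.00 and the simulated size is 4.8-5.1%. With 0, 1 and 2 events in 40, 20 and 40%, φ = 0.80 and the size is 2.8-3.1%.

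**Non-zero-only tests, if Poisson.** Under zero-inflated Poisson the non-zero counts are zero-truncated Poisson with ratio 1 + λ − λ/(1 − e^−λ), which is always below 1. At λ = 2 it is 1 + 2 − 2.313 = 0.687, giving a size of 1.8%. Under negative binomial counts the simulated size (4,000 trials per setting) goes either way: 0.1-5% at mean 0.5, 1.6-19% at mean 1 and 8-37% at mean 2, depending on how much patients differ.

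**Remedies.**

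- Sandwich variance brings the all-patient Poisson test to 4.6-6.2% in the overdispersed settings.
- Negative binomial regression with robust variance gives 4.4-6.2%. With model-based variance it falls to 0.9-1.2% at 60% structural zeros and mean 1.5.
- A Poisson model with a subject random intercept, fitted to one total per participant, gave 3.6-6.5% in six settings (800 trials each, 100 per arm, Monte Carlo SE 0.8 points). A smaller check (300 trials each, 120 per arm, SE about 1.3 points) gave 2.7-7.7%.

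**The case against.** **The random intercept may already cover the counts.** Hospitalizations and arrests are the primary outcomes, and the plan gives its primary outcome analysis a subject random intercept, which would restore roughly the nominal level. This stands as a possible reading. But the sentence follows the housing and recovery text, and it needs time and group-by-time terms. The only time points given are the assessments at baseline, 4, 8 and 12 months; no count intervals are defined. Two analysts could fit different models.

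**The plan may intend a two-part analysis:** any event or none, then the number among those with events. The count test would then be the non-zero one, which zero inflation makes conservative if it is Poisson. The intention-to-treat sentence weighs against this, because that comparison drops participants according to their outcome.

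**The size is not specific to this trial.** This is correct. Near φ = 1.1 the Poisson test is only slightly liberal, and the sandwich test is no clear improvement there.

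A reader might infer more than the documents support:

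- *That every count test is anti-conservative.* The non-zero-only tests have no named model. If Poisson, they are conservative under zero-inflated Poisson and can go either way under unequal rates.
- *That expecting zero inflation proves overdispersion.* The excess-zero examples above show otherwise.
- *That the CM/ICM split by county is the main source of unequal rates.* It affects controls only, and the Interventions section describes the two services as much alike. Even a threefold rate difference between them (assumed control mean 1, even split) gives φ = 1.25 in controls and 1 under ODR, with a simulated size of 6.2-6.3%. A twofold difference gives 5.3-5.6%.
- *That a false positive carries into a confirmatory claim against ICM.* The plan calls that comparison post hoc.

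**Conclusion.** The point holds for one test: the all-patient, intention-to-treat count comparison, if it uses model-based Poisson variance and no random intercept. That test is anti-conservative whenever the variance exceeds the mean. The direction is firm; the size is not. Over the assumed settings it runs from no inflation to a little over five times the nominal 5%, with about 8-9% at φ = 1.33, 16-17% at 2 and 26% at 3. The binomial any-or-none tests do not depend on this variance assumption, and the plan does not say whether the binary or the count test decides. This should be fixed, but it does not show that the trial's primary conclusions would be wrong.

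**What to change.** - Analyse the 12-month numbers of admissions and of arrests in all randomized participants with a log-link Poisson mean model and robust (sandwich) variance, or with negative binomial regression and robust variance. Report the rate ratio with its confidence interval.
- State whether the random-intercept sentence governs these counts. If it does, define the intervals that supply its time terms.
- Label the comparisons among participants with non-zero values as descriptive, and name their model.

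This takes a few sentences in the plan and standard software, with no new data. The cost is wider intervals, and some loss of apparent power, when counts are overdispersed. The sandwich test can also be slightly liberal in small arms (about 6% at 60 per arm).

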### Referral, Assessment, and Randomization

All procedures will be reviewed and approved by the university's and the State's Institutional Review Boards. Clinicians at the three sites will refer potentially eligible patients who will then be evaluated for their interest in taking part in the study and capacity to give informed consent. Trained research assessors will complete the initial/baseline assessment

within about a week before discharge. After eligibility screening, consent, and the assessment, the patient will be randomized at a 1:1 ratio to ODR or CM using a computer-generated algorithm. The study statistician will create the randomization list, by randomly alternating blocks of 2 or 4, and the resulting sequential treatment assignments will be sealed in opaque envelopes. After the patient is found to meet eligibility criteria, gives informed consent, and completes the baseline assessment, the research assessor will open the next envelope in the sequence and inform the ODR or CM provider of the treatment assignment.

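### The hospitalization models name no baseline covariate, although referral facility is known for everyone before randomization; the comparison is valid but may be less efficient than it could be

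*Combined protocol and SAP*

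**What the plan says.** Outcome Data Collection makes hospitalizations a primary outcome, together with arrests. Data Analyses gives the models: "Analyses involving hospitalizations and arrests will be performed using both binomial and Poisson generalized linear models for binary outcomes and counts, respectively". No predictor is listed in that sentence. The only model terms named anywhere in the section come later: "the model structure will include group (ODR vs. CM), time, and group-by-time interactions, with a random intercept for subject". It is unclear whether that sentence governs the hospitalization models or only the mixed models for housing and recovery. On either reading, no baseline covariate enters the hospitalization analysis.

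Two items of pre-randomization information bear on this:

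- **Referral facility.** Participants come from "a state psychiatric hospital in Savannah, Georgia; a crisis stabilization unit (CSU) in Savannah; and a CSU in Brunswick, Georgia".
- **Prior admissions.** The fourth eligibility criterion under Participants requires "two separate inpatient admissions, each for" at least two days, in the past 12 months.

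Under Referral, Assessment, and Randomization, patients are "randomized at a 1:1 ratio to ODR or CM using a computer-generated algorithm", with the list built "by randomly alternating blocks of 2 or 4". No stratification factor is named.

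**The concern.** A state hospital and two crisis units plausibly discharge people with different readmission risk, and past admissions plausibly predict future ones. Blocks of 2 or 4 keep the arm totals close but do not balance facility or prior use. If these variables predict 12-month hospitalization, leaving them out discards information that is at least partly in hand. The document states no numerical sample size, power or effect size, so nothing shows that power is ample.

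The plan is also uneven. The housing and recovery models use the baseline measurement as one of their four timepoints, and the recovery summary score is built expressly to save power. The primary hospitalization outcome has no comparable use of baseline information.

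**Working it through.** **Inputs.** From the document: binomial and Poisson models, 1:1 allocation, blocks of 2 or 4, three facilities, at least two prior-year admissions, 12-month endpoint. It gives no sample size, alpha, power, event rate, dispersion or correlation, so there is no stated figure to reproduce. Everything below is illustrative.

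**Step 1: linear-model approximation.** Let r be the correlation of the covariates with the outcome (assumed), with two-sided alpha 0.05 and 80% unadjusted power (both assumed).

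- Variance factor = 1 − r²
- Equivalent extra participants = 1/(1 − r²) − 1
- Power = Φ[(1.960 + 0.842)/√(1 − r²) − 1.960]

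For r = 0.4: 2.802/√0.84 = 3.057; 3.057 − 1.960 = 1.097; Φ(1.097) = 86.4%.

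| r | Variance reduction | Equivalent extra participants | Power |
|---|---|---|---|
| 0 | 0% | 0% | 80.0% |
| 0.1 | 1% | 1.0% | 80.4% |
| 0.2 | 4% | 4.2% | 81.6% |
| 0.3 | 9% | 9.9% | 83.6% |
| 0.4 | 16% | 19.0% | 86.4% |
| 0.5 | 25% | 33.3% | 89.9% |

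**Step 2: does this carry over to the models named?** The r² rule belongs to linear models, so it was checked by simulation: up to 600 trials per scenario, 240 participants, 1:1 in blocks of 2 or 4, about one admission per year, gamma frailty with variance 1, prior count of at least 2, three facilities, rate ratio 0.65. All of these except the allocation scheme, the eligibility threshold and the number of facilities are assumptions. Each cell shows unadjusted → adjusted for log prior count and facility. The first column is the correlation with the prior count alone.

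Poisson model, log rate ratio:

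| Correlation | Model-based SE | Robust SE | Spread of estimates | Power, robust SE |
|---|---|---|---|---|
| 0.00 | 0.147 → 0.147 | 0.194 → 0.194 | 0.199 → 0.200 | 0.575 → 0.578 |
| 0.11 | 0.146 → 0.147 | 0.196 → 0.194 | 0.198 → 0.197 | 0.592 → 0.600 |
| 0.25 | 0.143 → 0.144 | 0.206 → 0.197 | 0.207 → 0.205 | 0.548 → 0.590 |
| 0.37 | 0.137 → 0.138 | 0.224 → 0.202 | 0.238 → 0.217 | 0.502 → 0.580 |

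The model-based SE does not shrink. The gain shows only in the robust SE, and clearly only at the higher correlations.

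Logistic model, log odds ratio:

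| Correlation | Estimate | SE | Power |
|---|---|---|---|
| 0.00 | −0.432 → −0.437 | 0.262 → 0.266 | 0.352 → 0.387 |
| 0.25 | −0.424 → −0.445 | 0.263 → 0.272 | 0.380 → 0.373 |
| 0.37 | −0.406 → −0.445 | 0.263 → 0.278 | 0.313 → 0.353 |

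Adjustment raises the SE and moves the estimate away from zero, because the conditional odds ratio is a different quantity from the marginal one. The power changes are inconsistent. A rise of 0.035 appears even with no association, and the simulation error of one proportion near 0.37 is √(0.37 × 0.63/600) = 0.020. No reliable gain can be read from these figures. A standardized risk difference or ratio was not simulated.

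**Step 3: null case.** With rate ratio 1 and the same frailty, the plain Poisson test rejected in 17% to 28% of trials, with or without covariates. The robust test rejected in 5.7% to 8.7%.

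**Step 4: is the prior count available?** Criterion 4 can be met by confirming two admissions; nothing says that a full count is kept. Outcome Data Collection describes admission data for the study period. The State agency holds crisis-unit data only from January 2017, while enrollment starts in December 2014, and the year before enrollment is not mentioned. Only referral facility is certain to exist for everyone.

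**The case against.** The strongest reply is that an unadjusted randomized comparison is a legitimate choice and that the gain may be close to nil. Everyone enrolled has at least two recent admissions, which narrows the range of the prior count and may weaken its correlation with outcome. Nothing in the document shows that facility predicts readmission. At r = 0.1 the gain in power is 0.4 percentage points. Added to a plain Poisson model, the covariates would not even reduce the reported SE. All of this stands. It limits the size of the point and shapes the fix, but it does not remove the case for naming in advance a covariate that is certain to be available.

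A reader might infer more than the document supports:

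- **That the number of prior admissions is known for every participant.** Eligibility guarantees a check against a threshold, not a recorded count.
- **That the omission biases the comparison or inflates type I error.** It does neither. Chance imbalance is already covered by a correct standard error.
- **That the analysis ignores a design factor.** Facility is not a stratification factor, so design and analysis do not conflict.
- **That precision is being given away at no cost.** The gain depends on an unstated correlation and on the variance estimator, and one covariate may need new data extraction.

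**Conclusion.** The point holds as an efficiency improvement to a primary analysis, not as a validity defect. The plan names no baseline covariate for the hospitalization models, and at least one candidate is known for all participants before randomization. A variance reduction of about 1% to 25%, with nominal 80% power becoming about 80% to 90%, rests wholly on an assumed correlation of 0.1 to 0.5 and on a linear-model approximation. If the covariates are not prognostic, there is no gain. For counts, the simulation supports the direction when a robust variance is used; for the odds ratio it shows no dependable benefit. The absence of any stated handling of overdispersion is a separate matter and, under the assumptions used here, probably the larger one.

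**What to change.** Amend Data Analyses so that the binary and count hospitalization models for all randomized participants:

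1. include referral facility (three levels) as a fixed covariate and, if captured for every participant, the log of the number of admissions in the 12 months before enrollment;
2. use a robust or overdispersion-corrected variance for the count model;
3. report, for the binary model, a standardized (marginal) risk difference or ratio, so that the target remains the comparison of the randomized arms;
4. keep the unadjusted result as a sensitivity analysis.

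The plan should also state whether the exact prior-year count is recorded and from which source. The document is dated 2022 and revised in 2024, while enrollment was to start in December 2014 and last about three years. If outcomes by arm had been seen before this change, label the adjusted result supplementary.

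Cost: SAP wording and up to three extra coefficients (two for facility, one for the count), plus possibly an extraction of pre-enrollment admissions if screening did not record the number.
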